
There will be a three-week interval between the first and the second (last) testing sessions. Participants randomized to the control group will be encouraged to continue with their usual and customary exercise program. Participants in the exercise group will be instructed on performing a targeted phantom exercise program to be included in their usual and customary exercise program. At the second testing session, the same researcher will repeat all baseline measures. All data collection, including screening questionnaires and surveys of the study, will be performed through the secure REDCap platform (<https://www.project-redcap.org/>).

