Physical function assessments will be done by performing targeted phantom motor executions and four-square step test (FSST). Muscle activity will be recorded for the targeted phantom motor executions while participants are not wearing their prosthesis. However, the assessment of FSST needs participants to wear their prosthesis without EMG recording. The justification for this decision is preventing the risk of injury at the skin-prosthesis interface due to electrodes and wires. Foot plantar load will be assessed during targeted phantom motor executions and FSST. Participants will rest 2 minutes while sitting in a chair after each physical function assessment (4 minutes in total). This time will be used to instruct the participant in the testing protocol. Additional time will be provided if requested by the participant. After baseline testing is complete, EMG electrodes and sensors for the foot plantar load will be removed. Participants will then be informed of their randomization group that was determined earlier (before their baseline assessment) using the block and simple randomization techniques.

Collected data for the morphology of the residual limb, phantom phenomena, TAPES-R, PEmbS-LLA, physical function assessments, and muscle activities of the first session are baseline data and will be used for comparison to the results of the same measurements of the second session. After the first session, participants in the exercise group will be enrolled in the targeted phantom limb exercise program in addition to continuing with their usual and customary post-amputation care while participants of the control group will continue with their usual and customary post-amputation care. Participants in the exercise group will be trained on the targeted phantom limb exercise program and will have specific training sessions for three weeks at participants' homes via Zoom (<https://zoom.us/>). The researcher will make Zoom video calls to supervise participants and get assurance that all instructions are followed. After three weeks, participants of both groups will attend the test center for the second testing session. For both testing sessions, the same researcher captures the shape of the residual limb, surveys the phantom phenomena, TAPES-R, and PEmbS-LLA, assesses physical function, and conducts EMG investigations.

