#### ***Data analysis and statistics***

Different levels of comparisons will be done to explore the impact of the targeted phantom motor execution program on phantom phenomena and physical function of people with TTA. Before starting analyses, the normality of distribution of the quantitative variables will be assessed by the Shapiro-Wilk test. Since there are two groups of participants, whether participants are matched on their demographic and clinical characteristics will be explored using independent t-test and chi-square statistics. Based on our expectation of normality of distribution for the quantitative variables, if it is the case, parametric statistical tests will be used. An independent t-test will be used to compare quantitative variables within-subjects for the amputated and non-amputated sides. Similarly, Mann-Whitney test and Chi square test will be used respectively to compare ordinal and nominal categorical variables within-subjects for the amputated and non-amputated sides. An independent t-test will be analyzed to compare quantitative variables between the two groups. Similarly, Mann-Whitney test and Chi square test will be used respectively to compare ordinal and nominal categorical variables between the two groups.

Two-way analysis of variance can be used to compare the simultaneous effect of groups assignment and prosthesis embodiment on PLC. Similarly, Friedman's two-way analysis of variance will be used to compare the simultaneous effect of group assignment and surgical closure on PLC.

Spearman's correlation coefficients will be calculated to explore the potential relationship of phantom phenomena responses with participants' characteristics (i.e. age, weight, height, body mass index, length of the residual limb, the circumference of the residual limb, time after amputation, and years of prosthesis use). Moreover, the potential relationship of the phantom phenomena responses with participants' gender, type of surgery, and footedness will be explored by point-biserial correlation assessment. The potential

relationship of the phantom phenomena responses with participants' prosthesis type will be explored by partial eta square correlation assessment.

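### For quantitative outcomes, the between-group t-test does not say whether it compares second-session values or change, and no analysis lists the outcome's own baseline value; ANCOVA would settle the choice and is usually more precise.

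*Combined protocol and SAP*

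**What the plan says.** Outcomes are measured twice, three weeks apart. Experimental setup states "At the second testing session, the same researcher will repeat all baseline measures". Experimental protocol adds that the first-session measurements "are baseline data and will be used for comparison to the results of the same measurements of the second session".

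The between-group analysis in Data analysis and statistics is one sentence for quantitative outcomes, "An independent t-test will be analyzed to compare quantitative variables between the two groups", and one for the rest: "Mann-Whitney test and Chi square test will be used respectively to compare ordinal and nominal categorical variables between the two groups". Neither names a session or a change score.

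The other analyses that involve group are:
- "Two-way analysis of variance can be used to compare the simultaneous effect of groups assignment and prosthesis embodiment on PLC";
- Friedman's "two-way analysis of variance will be used to compare the simultaneous effect of group assignment and surgical closure on PLC";
- linear regressions of physical function on clinical and demographic characteristics and group;
- logistic regressions of phantom phenomena on the same predictors plus physical function measures.

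Clinical characteristics are not defined for the regressions. Where the section does list participant characteristics, for the correlations, it gives "age, weight, height, body mass index, length of the residual limb, the circumference of the residual limb, time after amputation" and years of prosthesis use. None of these is a physical function measure.

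**The concern.** The trial asks whether a three-week program changes outcomes that are measured before and after it. With one baseline and one follow-up value, a between-group t-test can compare follow-up values or changes. These are different estimators, and which is more precise depends on the correlation between the two sessions. The plan does not choose, and it does not list the third option, which uses the baseline value as a covariate.

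Two things are at stake. The first is power, because either t-test may turn out to be the poor choice for a given outcome. The second is the error rate: if the choice is made after the data are seen, the stated 5% threshold no longer describes the procedure.

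**Working it through.** **Inputs from the document.** Two parallel randomized arms, two sessions three weeks apart, significance at p < 0.05 (taken as two-sided).

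**Assumptions.** The available text gives no sample size, effect, SD, correlation or allocation ratio, so there is no stated figure to reproduce. I assume 1:1 allocation, n per arm from 6 to 30, equal SDs at both sessions, bivariate normal data, correlation ρ from 0 to 0.95, and an effect of 0.7 SD unless stated otherwise.

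**Step 1: does any analysis use the outcome's baseline?** Taking the listed analyses in turn: the t-test names no session; the two-way analysis of variance has group and embodiment; Friedman's has group and surgical closure; the regressions have characteristics, group and, for the logistic model only, physical function. There is no paired test, change score, group-by-session model or baseline covariate. The comparison announced in Experimental protocol is therefore not assigned to any test.

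**Step 2: variance of the group difference, relative to the second-session t-test (= 1).**
- Change: 2(1 − ρ).
- ANCOVA: (1 − ρ²)k, where k = 1 + 1/(2n − 4) is the cost of estimating the slope.

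At n = 20, k = 1 + 1/36 = 1.028. At ρ = 0.5, change is 2 × 0.5 = 1.00 and ANCOVA is 0.75 × 1.028 = 0.771. At ρ = 0.7, change is 0.60 and ANCOVA is 0.51 × 1.028 = 0.524. The two t-tests are equally precise only at ρ = 0.5.

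**Step 3: power at 20 per arm, 0.7 SD** (simulation, 40,000 trials per cell; gains taken before rounding).

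| ρ | Second session | Change | ANCOVA | Gain over change | Gain over second session |
|---|---|---|---|---|---|
| 0.3 | 58% | 45% | 61% | 16 | 3 |
| 0.5 | 58% | 58% | 69% | 11 | 11 |
| 0.7 | 58% | 80% | 85% | 5 | 27 |
| 0.8 | 58% | 93% | 94% | 2 | 36 |

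The exact second-session t-test power is 57.8%. At 10 per arm the pattern is the same: second session 32%; change 24 / 31 / 48 / 64%; ANCOVA 33 / 38 / 52 / 67%.

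**Step 4: where ANCOVA loses.** On variance, it loses to second-session values when ρ < √(1 − 1/k) and to change when ρ > 2/k − 1. It therefore has the lowest variance of the three between these limits:
- 6 per arm: 0.33 and 0.78
- 10 per arm: 0.24 and 0.88
- 20 per arm: 0.16 and 0.95
- 30 per arm: 0.13 and 0.96

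Outside these limits the power losses are small:
- 10 per arm, ρ = 0: about 1.5 points at 0.7 SD and 2.7 at 1.0 SD.
- 6 per arm: about 4-5 points at 1.2 SD with ρ = 0, and about 3 points against change at 0.7 SD with ρ = 0.9.

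**Step 5: the open choice.** Under no effect, each of the three tests used alone holds about 5%. Reporting the smaller p-value of the two t-tests gives 8.5-9.7% for ρ from 0.3 to 0.8 and 10 to 30 per arm. With a 0.7 SD effect and 20 per arm, the two t-tests disagree on significance in 32 / 33 / 37 / 40% of trials at ρ = 0.3 / 0.5 / 0.7 / 0.8.

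**Step 6: chance baseline difference.** Its SD is √(2/n), which is 0.316 at n = 20, so a difference above 0.3 SD has probability 34%. At ρ = 0.7, a 0.3 SD difference moves the second-session estimate by 0.7 × 0.3 = 0.21 SD and the change estimate by (0.7 − 1) × 0.3 = −0.09 SD. ANCOVA removes both shifts.

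**Step 7: a baseline measurement affected by allocation.** Suppose baseline readings in one arm are shifted by an assumed 0.3 SD with no true effect, at 20 per arm and ρ = 0.7. Type I error is then about 14% for ANCOVA, 22% for change and 5% for second-session values.

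**The case against.** Four objections carry weight.

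- **The plan probably means change.** The Experimental protocol sentence points that way. This stands as the likelier reading, and the gain to expect is then the smaller set (16 / 11 / 5 / 2 points), not 36. It does not settle the matter, because the analysis section names no change score. Simply naming one t-test would close the open choice; preferring ANCOVA is a further argument about precision.
- **Baseline might be among the clinical characteristics.** The term is undefined, and the opening part of the document was not available for this review. So the statement must be that no analysis lists the baseline value, not that the sponsor has ruled it out.
- **Small arms could erase the gain.** No sample size is available, so arms as small as 6 cannot be excluded. There the favourable range narrows to correlations of 0.33 to 0.78.
- **Baseline may not be clean.** The group is assigned at the end of the phone interview, before baseline testing, in a non-blinded trial. Participants learn it only afterwards ("Participants will then be informed of their randomization group that was determined earlier"), but the researcher already knows it. ANCOVA and change both need baseline measurements unaffected by that knowledge; a second-session t-test does not. This trade-off is real and belongs in the cost.

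A reader might also infer that the planned t-test is biased or invalid. The document does not support that: under randomization, either version, chosen in advance, holds its error rate.

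**Conclusion.** The point holds for quantitative outcomes, as a matter of precision and an unfixed choice. The compared quantity is unstated, and an available covariate that usually helps is not listed. The direction of the gain is secure over most of the plausible correlation range. Its size is not, because sample size, correlation, effect, equal SDs and 1:1 allocation are all assumed. The inflation to about 9-10% applies only if the more favourable t-test is picked after the data are seen; the document does not say that this will be done, only that nothing prevents it. The change is a cheap improvement that should be made, not a correction of an invalid analysis.

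**What to change.** In Data analysis and statistics:

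1. Replace the between-group t-test for each quantitative outcome with ANCOVA of the second-session value on group and the baseline value of the same outcome, and report the adjusted difference with its 95% CI. With baseline in the model, using change as the response gives the same group difference, so the choice disappears.
2. Judge normality on the model residuals. If it clearly fails, use the same model on ranks.
3. State that the response in the linear regressions that include group is the second-session value, and add its baseline value as a predictor.
4. State that the between-group Mann-Whitney and chi-square tests, and the PLC analyses by group, use second-session values.
5. Report the unadjusted second-session difference as a sensitivity analysis, because it alone does not depend on baseline being unaffected by known allocation.

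**Cost.** This is a wording change to be made before the data are seen. Baseline is already collected, and ANCOVA is available in the planned software. It uses one degree of freedom per outcome, assumes a roughly linear relation with baseline, and accepts the small power losses shown above when the correlation is near 0 or above about 0.9. It also relies on baseline measurements unaffected by allocation, which item 5 is there to check.

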### ***Experimental setup***

This research is a 2-arm, parallel, open label, non-blinded randomized controlled trial comprised of four independent but interrelated studies with the same participants. The familiarization phase, enrollment verification, obtaining verbal consent to participate, and gathering screening information will be done via phone interview. After screening participants, the Medical and Demographic Questionnaire will be administered. The participant will be e-mailed a link to complete the following surveys/questionnaires: Medical and Demographic questionnaire, Waterloo Footedness Questionnaire to determine their dominant lower extremity, and The Survey of Phantom Limb Awareness and Control that is a commonly used questionnaire regarding phantom phenomena. The participant can use a smartphone, iPad or computer to answer these surveys/questionnaires. Completion of the surveys/questionnaires at the home will respect COVID-19 restrictions by diminishing time spent with the researcher. If the participant is not able to complete the surveys/questionnaires prior to their first scheduled visit, they will be given the opportunity to do at WinPO prior to the physical function evaluation. At the conclusion of the phone interview, the researcher will randomly assign participants to the control or exercise groups. Participants in both groups will then be scheduled for an in-person baseline visit and an in-person follow up visit at WinPO for data collection. The baseline visit will begin with review of expectations and the participant will sign informed consent. All information gathered at the phone interview will be reviewed for accuracy. If the participant has not answered the questionnaires/surveys prior to their baseline visit, they will be provided an iPad to complete the Medical and Demographic Questionnaire, Waterloo Footedness Questionnaire, and The Survey of Phantom Limb Awareness and Control. The baseline testing session will be entirely the same for participants of both groups. During this session, the researcher will assess participants based on their anthropometric variables (i.e. height, weight, body mass index), the morphology of the residual limb (i.e. length, circumference, and volume),—prostheses embodiment as measured by TAPES-R and PEmbS-LLA, and functional abilities as measured by targeted phantom motor execution and FSST, while recording their muscle activities and plantar foot loads. After completion of the baseline testing, the researcher will contact [name], to get information with respect to what surgical closure technique was performed for the participant.

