### ***Experimental protocol***

At the beginning of the baseline testing session, the researcher measures participants' weight and height using a scale and stadiometer; the body mass index will be calculated using REDCap programmed formula. Then the researcher will survey prosthetic embodiment by asking participants to fill out the revised version of the Trinity Amputation and Prosthesis Experience Scales (TAPES-R) and Prosthesis Embodiment Scale for Lower Limb Amputees (PEmbS-LLA), which are brief self-administered questionnaires to assess the adjustment and interaction of people with amputation to their prosthesis. Then, the researcher will ask participants to sit on a chair within parallel bars and remove their prosthesis. The researcher will examine the residual limb and places paper skin markers on specific landmarks over their residual limb (i.e. middle of the patella, tibial tuberosity, the distal end of the residual limb). Then, participants will stand securely inside parallel bars while the researcher captures the shape of their residual limb using a 3D scanner (OMEGA Scanner 3D, Willow Wood, Ohio, USA). The morphologic characteristics of the residual limb (i.e. length, circumference, and volume) will be recorded. If the participant finds it difficult to stand without the prosthesis, the scan will be performed in sitting and note in the assessment. The participant will then return to the sitting position and placement for the electromyography (EMG) electrodes (Trigno, Delsys Inc., Massachusetts, USA) will be determined on both the intact and amputated limbs based on the standard electrode placement guideline. However, for the amputated side, since the length of the muscles has changed, the location of the EMG electrodes needs to be determined specifically for each participant based on the new muscle bulk and optimal electrical signal activity. Electromyography of the tibialis anterior, medial and lateral heads of the gastrocnemius muscle will be recorded for both sides. Electrode locations will be marked and photographed to ensure consistency with subsequent testing session recordings. The skin will be cleaned using an alcohol pad and electrodes will be attached using paper tape.

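### Prosthesis embodiment enters the two-way ANOVA on PLC with no instrument, session or grouping named; a model with continuous session-1 embodiment would be better

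*Combined protocol and SAP*

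**What the plan says.** The analysis in question is one sentence in *Data analysis and statistics*: "Two-way analysis of variance can be used to compare the simultaneous effect of groups assignment and prosthesis embodiment on PLC".

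The earlier sections describe the embodiment variable. *Experimental setup* lists "prostheses embodiment as measured by TAPES-R and PEmbS-LLA" among the baseline assessments, so there are two instruments. *Experimental protocol* describes them as tools "which are brief self-administered questionnaires to assess the adjustment and interaction of people with amputation to their prosthesis". The text available for review gives no category, cut-off or scoring rule for either.

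Both instruments are given twice. *Experimental setup* states: "There will be a three-week interval between the first and the second (last) testing sessions", and then: "At the second testing session, the same researcher will repeat all baseline measures". *Experimental protocol* is more specific. At each session the researcher "surveys the phantom phenomena, TAPES-R, and PEmbS-LLA, assesses physical function, and conducts EMG investigations". It also lists TAPES-R and PEmbS-LLA among the session-1 data that "are baseline data and will be used for comparison to the results of the same measurements of the second session".

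**The concern.** A two-way ANOVA compares means across the levels of two factors. Group assignment has two levels. Embodiment, as measured here, has none until someone defines them. The plan leaves three choices open: the instrument, the session, and the rule that turns a score into levels.

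Two things are at stake.

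- **Information on embodiment.** Grouping a score discards part of what it says about PLC. This weakens the embodiment effect and its interaction with group, which are the reason for running this analysis. A grouping rule left open can also be chosen after the data are seen.
- **Meaning of the group effect in this model.** The plan compares embodiment between sessions, so it allows that embodiment may change. If the factor were built from session 2, the model would condition on something measured after the programme, and possibly altered by it.

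**Working it through.** The plan states no figure on this point, so there is none to reproduce. The check has three parts.

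**1. What is open.** Two instruments and two sessions give 2 × 2 = 4 candidate scores before any grouping rule is chosen. The sentence on the ANOVA does not select among them.

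**2. Cost of grouping (illustrative).** Assume a normally distributed score with a linear relation to PLC. Cut it so that a fraction q lies above the cut point c, and let φ be the standard normal density. The share of the explained variance that is kept is

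φ(c)² / [q(1 − q)].

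For a median split, q = 0.5 and c = 0, so φ(0)² = 1/(2π) = 0.159. The share kept is 0.159 / 0.25 = 2/π = 0.637. The correlation is multiplied by √0.637 = 0.798. The number of participants needed for the same information on embodiment rises by π/2 = 1.57.

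| Split | Share of explained variance kept |
|---|---|
| 1/2 vs 1/2 | 64% |
| 1/3 vs 2/3 | 59% |
| 1/4 vs 3/4 | 54% |
| 1/5 vs 4/5 | 49% |

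These figures concern the embodiment term only.

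**3. Effect of the session chosen (illustrative).** The simulation used 400,000 participants and an additive two-way model. All inputs are assumptions:

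- direct group effect on PLC of 0.5;
- effect of exercise on session-2 embodiment of 0, 0.3, 0.5 or 0.8 within-group standard deviations;
- effect of embodiment on PLC of 0 or 0.3 per unit;
- with or without an unmeasured cause shared by session-2 embodiment and PLC.

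With mediation only and an exercise effect of 0.5, the total effect should be 0.5 + 0.3 × 0.5 = 0.65, and the simulation returns 0.65. The results for an exercise effect of 0.5 on embodiment are:

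| Scenario | Total randomised effect | Model with session-1 split | Model with session-2 split |
|---|---|---|---|
| Mediation only | 0.65 | 0.65 | 0.56 |
| Mediation and shared cause | 0.65 | 0.65 | 0.49 |
| Shared cause only | 0.50 | 0.50 | 0.39 |

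Over exercise effects of 0.3 to 0.8, the session-2 split shrank the group effect by between 1 − 0.531/0.587 = 10% and 1 − 0.320/0.496 = 35%. With no effect of exercise on embodiment, the session-2 split left it unchanged (0.50 against 0.50). The session-1 split left it unchanged in every scenario.

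**The case against.** The strongest reply is that this is an exploratory analysis described permissively. The sentence says the method can be used, not that it will be, and nothing in the available text marks it as primary. The randomised comparison does not depend on it: the same section separately plans a t-test, Mann-Whitney or chi-square test between groups, none of which involves embodiment. That stands, and it limits the consequence to the embodiment question and to the group effect as read from this one model.

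A reader might infer more than the documents support in four ways.

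- *That the plan dichotomises embodiment at an arbitrary point.* No split is described. Levels could come from a scale's own categories, or each distinct score could be a level, though that would leave nearly empty cells. What is established is that levels are needed and none are defined. A cut-off fixed in advance would end the post hoc choice, but would not recover the lost information.
- *That the group effect on PLC is biased.* No section says that the session-2 score will be used. Even if it were, the simulation shows no distortion when the programme leaves embodiment unchanged.
- *That the trial needs 1.57 times as many participants.* The factor applies to information on embodiment, under normality and a median split. It does not apply to the randomised comparison.
- *That a continuous score is better whatever the relation.* If PLC changed at a threshold of embodiment, grouping could fit better than a straight line. This is why linearity should be checked.

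**Conclusion.** The point holds in a limited form. The plan names a method that needs factor levels for a variable measured as a questionnaire score, and fixes neither the instrument, the session nor the levels. This is more than a missing detail, because a better analysis is available from data already being collected.

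The size can only be illustrated. About 36% of the variance explained by embodiment (1 − 0.637) would be lost under a median split of a normal score with a linear effect, and more under uneven splits. The group effect in this model would shrink by about 10% to 35% if the session-2 score were used and the programme shifted embodiment by 0.3 to 0.8 standard deviations, under the assumed links to PLC. Neither figure comes from the documents. The second is conditional on a choice that the plan has not made.

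The change should be made before the data are analysed. It does not call the separate between-group tests into question.

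**What to change.** Replace the two-way ANOVA of PLC on group and embodiment with a regression (ANCOVA) of session-2 PLC on:

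- group;
- baseline PLC;
- the session-1 embodiment score, continuous and centred, from one instrument named in advance (TAPES-R or PEmbS-LLA, with the subscale or total to be used);
- the group-by-embodiment interaction.

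With centring, the group coefficient is the effect at average embodiment. Use ordinal regression if PLC is ordinal and logistic regression if it is binary. In those models the group odds ratio is conditional on the covariates and need not equal the unadjusted one. State which applies. The session-1 score is a safe covariate because it is collected before the programme starts and before participants are told their group.

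Label any analysis that uses session-2 embodiment as exploratory or as a mediation analysis. Surgical closure need not be added to this model.

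The cost is wording only. The data, visits and software are unchanged, and the plan already includes linear and logistic regression. Compared with a 2 × 2 layout, which has three effects, the model for a numeric PLC has four coefficients besides the intercept, the extra one being baseline PLC. The small downside is the assumed linear effect of embodiment, which should be checked with a plot.

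### Friedman's test is named for the joint effect of group and surgical closure on PLC, but both factors vary only between participants, so the test cannot assess both

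*Combined protocol and SAP*

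**What the plan says.** The section *Data analysis and statistics* pairs two joint analyses of PLC (neither the abbreviation nor its scale is defined in the available text). The first is: "Two-way analysis of variance can be used to compare the simultaneous effect of groups assignment and prosthesis embodiment on PLC". The next sentence applies a different method to closure: "Similarly, Friedman's two-way analysis of variance will be used to compare the simultaneous effect of group assignment and surgical closure on PLC".

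Other sections fix the structure of the data:

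- **Group.** *Experimental setup* says "This research is a 2-arm, parallel, open label, non-blinded randomized controlled trial", and that "the researcher will randomly assign participants to the control or exercise groups". Each person is in one arm only.
- **Closure.** After baseline testing the researcher makes an enquiry "to get information with respect to what surgical closure technique was performed for the participant". This is one past fact per person. *Experimental protocol* says electrode placement "will be determined on both the intact and amputated limbs", so each participant has one amputated limb and one closure.
- **Repetition.** "At the second testing session, the same researcher will repeat all baseline measures". The phantom measures are therefore taken twice, three weeks apart. The Friedman sentence does not mention session.

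**The concern.** The words two-way in the name of Friedman's test refer to condition by block. They do not mean two tested factors. The blocks are a nuisance: ranking within them removes their effect, and the test gives no result for the block and none for an interaction. It is not a rank version of a factorial analysis of variance for independent groups, which is how the plan appears to use it.

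The plan therefore commits to a test that cannot answer its own question. An analyst who follows it must choose a layout that the plan does not describe. Depending on that choice, the output says whether PLC changed between sessions with the arms pooled, or tests one factor on data collapsed to one value per cell. Either result could be reported as a joint effect of group and closure.

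**Working it through.** The plan gives no sample size, power or effect size for this analysis in the available text, so there is no figure to reproduce. The check goes through each layout that Friedman's test would accept. The plan supplies the 0.05 significance level, the two arms and the two sessions. The numbers of participants, the effect sizes and the number of closure types are assumptions.

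**Layout 1: participants as blocks, the two sessions as conditions.** Neither group nor closure varies within a block, so neither enters. With two conditions and no ties the statistic is Q = (2X − n)²/n on 1 df, where X is the number of participants whose PLC rose. This is a sign test on the pooled arms. Assume normal changes with SD 1 and equal arms. A mean change of 0.8 SD gives each participant a probability Φ(0.8) = 0.788 of rising. For n = 40, p < 0.05 requires X ≥ 27 or X ≤ 13. Exact binomial rejection rates are:

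| n | Both arms +0.8 SD (group effect zero) | Arms +0.8 and −0.8 SD (group effect large) | No change |
|---|---|---|---|
| 20 | 76.4% | 1.3% | 4.1% |
| 40 | 96.9% | 1.1% | 3.8% |
| 60 | 99.8% | 1.7% | 5.2% |

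The test rejects when there is no group effect and almost never when there is a large one. It is answering a question about session.

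**Layout 2: closure types as blocks (b of them), group as condition (k = 2), one value per cell.** Q = 12/[bk(k+1)] × ΣR² − 3b(k+1), where R are the rank sums. If the same arm is higher in every block, the rank sums are b and 2b, and Q = 10b − 9b = b, its maximum. The smallest exact p is 2/2^b.

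| Closure types b | Largest Q | Smallest asymptotic p | Smallest exact p |
|---|---|---|---|
| 2 | 2 | 0.157 | 0.50 |
| 3 | 3 | 0.083 | 0.25 |
| 4 | 4 | 0.0455 | 0.125 |
| 5 | 5 | 0.025 | 0.0625 |
| 6 | 6 | 0.014 | 0.031 |

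So p < 0.05 is out of reach with two or three closure types, and by the exact test with fewer than six. Closure itself is not tested: adding 100 to every value in one closure block leaves the within-block ranks, and so Q = 2 for b = 2, unchanged. Interaction is not tested either: opposite group effects in two closure types give rank sums of 3 and 3, and Q = (12/12) × 18 − 18 = 0.

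**Layout 3: the two groups as blocks, closure types (k) as conditions.** The largest Q is 2(k − 1) on k − 1 df, and the smallest exact p is 1/k!. For k = 2 these give 0.157 asymptotic and 0.50 exact; for k = 3, 0.135 and 0.167; for k = 4, 0.112 and 0.042. Group is now the untested factor.

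**Could the design supply real blocks?** It describes no crossover and no matching of participants. Its check of baseline comparability uses independent t-tests and chi-square tests. The block randomization mentioned under *Experimental protocol* is a method of allocation and is not described as pairing participants across arms.

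**The case against.** The strongest reply is that the plan reaches the same information elsewhere.

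- *Data analysis and statistics* also correlates phantom phenomena with type of surgery, which may mean closure technique, and compares the two groups directly.
- Its logistic regression takes group together with clinical and demographic characteristics, and closure could count as one of these.
- The sentence asks for a simultaneous effect and never says interaction, so an additive model might satisfy it.
- The rejection rates and minimum p-values rest on layouts and sample sizes that the plan does not state.
- The comparisons are introduced as exploratory.

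Much of this is fair, and it limits the consequence. Marginal information on each factor may still be obtained, and the lack of an interaction test matters less than the inability to test both factors. But the correlation leaves out group, so it says nothing about a joint effect. The regression does not name closure or a group-by-closure term, and even if closure were included, the Friedman sentence would remain a commitment to an unsuitable test. The calculations are illustrations only; the mismatch follows from the design alone.

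**Conclusion.** The concern holds. Group and closure are both fixed within a participant, and Friedman's test, in any layout, tests at most one of them. This rests on the design description and on no assumed number. The percentages depend on assumed sample sizes, normal changes and equal arms; the minimum p-values depend on an assumed number of closure types and one value per cell.

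The damage is confined to this one comparison, which appears exploratory, and the direct two-group comparison is untouched. It should be fixed before analysis, because the test as named could give a significant result that has nothing to do with either factor.

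**What to change.** Delete the Friedman sentence and specify a between-participant factorial model: second-session PLC on group, closure type and group × closure, adjusted for baseline PLC. Use ANCOVA if PLC is quantitative, and ordinal or logistic regression if it is categorical; state the PLC scale so that the choice is settled in advance. Report group, closure and interaction estimates with 95% confidence intervals. If some group-by-closure cells are sparse, report the main-effects model and say that the interaction could not be estimated reliably. Because closure is not randomized, label its effect and the interaction as exploratory.

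The cost is one sentence of the plan. Closure and both PLC measurements are already collected, and the named SPSS package fits these models. The drawback is an imprecise interaction. In a balanced 2 × 2 layout with m participants per cell and residual SD σ, the group main effect averages two cell differences, so its standard error is √[(1/4)(4σ²/m)] = σ/√m. The interaction is the difference between those two differences, with standard error √(4σ²/m) = 2σ/√m, twice as large.
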